### 9.7.2 Unacceptable

- 9.7.2.1 Dose volume analysis of the target volume confirms  $< 90\%$  of the prescribed dose covering  $< 90\%$  of the PTV\_EVAL. The volume of trapped air/fluid will be accounted for using methodology described in Section 9.4.1.
- 9.7.2.2 Maximum skin dose exceeds 120% of the prescribed dose.
- 9.7.2.3 Maximum rib dose exceeds 120% of the prescribed dose.
- 9.7.2.4 The volume of breast tissue receiving 150% (V150) of the dose exceeds 40 cc.
- 9.7.2.5 The volume of breast tissue receiving 200% (V200) of the dose exceeds 17 cc.
- 9.7.2.6 DHI  $< 0.75$  (for multicatheter cases).

## 10. DISEASE CONTROL

The secondary endpoint of the study is local tumor control at 3 years. This will be assessed by physical examination and mammography. All cases of local failure must be proven using pathologic criteria. Note: Investigators are also asked to report any contralateral, regional (classified as an axillary, supraclavicular, internal mammary node, or skin recurrence) or distant

failure.

The location of the local ipsilateral failure in relation to the original cancer will be recorded. Criteria established by Recht et al. will be used to help classify the type of local in-breast recurrence as follows:

True Recurrence/Marginal Miss Failure (TR/MM): A TR/MM failure is defined as a recurrence of the treated cancer within or immediately adjacent to the primary tumor site.

Elsewhere Failure (E): An 'E' failure is defined as local recurrence several centimeters from the primary site and is generally believed to be a new primary cancer.

## **11. BREAST TOXICITIES**

The primary endpoint of the study is serious toxicity rates. This will be assessed by physical examination at each follow-up visit. To be scored as a serious toxicity counting toward the primary endpoint, the toxicity must have a "probable" or "definite" attribution to the study treatment. Possible reportable toxicities to monitor include (but are not limited to) the following:

### **11.1 Seroma Formation**

Investigators are asked to record information regarding seromas at each follow-up visit. Seromas are defined as transient, persistent, or symptomatic (e.g., causing pain or discomfort, and/or requiring therapeutic intervention) and will be monitored for (1) method of detection, (2) signs and symptoms, and (3) method of treatment.

### **11.2 Fibrosis**

Patients will be evaluated for subcutaneous fibrosis at each follow-up visit. Fibrosis will be graded as detailed in CTCAE v4 and described in detail in the Appendix (CRF 5).

### **11.3 Infection**

Investigators are asked to record information regarding infections at each follow-up visit. Infection will be evaluated for (1) method of detection, (2) location, (3) signs and symptoms, and (4) method of treatment.

### **11.4 Fat Necrosis**

Investigators are asked to record information regarding fat necrosis at each follow-up visit. Fat necrosis will be evaluated for (1) method of detection, (2) signs and symptoms, and (3) method of treatment. Fat necrosis however is not a CTCAE toxicity and will not contribute to the endpoint analysis.

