The Milan group, led by Vernonesi and Orrechia, has simultaneously studied a different technology for the same purpose: intraoperative radiotherapy with electrons (ELIOT). In the ELIOT technique, the breast margins are re-apposed intraoperatively and an intra-operative dose of 21 Gy is prescribed to the 90% isodose line with 3-12 MeV electrons. In the most recent update of the ELIOT trial, 1305 were randomized, 654 to the whole breast arm and 651 to the ELIOT arm^22. With a median follow-up of approximately 6 years, the 5-year ipsilateral breast tumor recurrence rate was 4.4% in the ELIOT arm and 0.4% in the whole breast arm ( $p<0.0001$ ). The corresponding 5-year “true” local recurrence rates were 2.5 vs 0.4% ( $p=0.0003$ ). Significantly higher rates of fat necrosis were seen with ELIOT (14% vs 7%,  $p=0.04$ ).

With the ELIOT approach, a homogenous dose is delivered to a target volume that is generally consistent with the target volumes treated in the accumulated APBI literature. However, the ELIOT approach is agnostic to final pathology findings; no “remedial” treatment is offered to women found to have positive margins or positive lymph nodes. The impact of positive margins on local failure is well documented. Margin-status from the primary lumpectomy specimens is not reported in the ELIOT data; however approximately 25% of patients in both groups were node-positive, with approximately 5% with pN2a disease (>3 positive nodes). The ELIOT results amply highlight the perils of poor patient selection that may come with intraoperative radiotherapy. Furthermore, the clinical fat necrosis rate in the ELIOT patients on the randomized trial was much higher (14%) than the 2.3% reported with balloon-device based APBI. This is almost certainly because the 21 Gy dose was arrived at using linear-quadratic formalism and an incorrect  $\alpha/\beta$  ratio of 10 for breast cancer. While acknowledging the imperfection of linear-quadratic assumptions at doses above 8-12 Gy, the ELIOT dose is almost double the 2 Gy equivalent-dose of fractionated courses of APBI. Thus the ELIOT experience as reported in the interim results of the randomized trial is fraught with not one but two major reasons for pessimism—suboptimal tumor control and higher toxicity.

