However, given that the IORT trials are large randomized trials, an important outstanding question for APBI is “Can the the APBI schedule be similarly shortened?”. Efforts at compressing the fractionation of applicator-based APBI to a 2-day treatment course have been reported from the William Beaumont Hospital and a collaborative multi-institutional effort reported earlier by our group. The Beaumont group reported on a cohort of 45 patients treated with 4 fractions of 7 Gy over 2 days. With a median followup of 3.7 years and a minimum follow-up of 2 years, only grade 1 and 2 toxicities were reported. The most common toxicities were: fat necrosis (18%) and asymptomatic seroma (42%). Three patients had rib fractures. In our first report of the “schedule seeking” Overnight Trial, we reported on 30 women treated on the first cohort of 7 Gy x 4 fractions. No grade 3 toxicities were noted; one breast infection, and 2 each cases of fat necrosis and symptomatic seromas were seen.

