## 15.3 Sample Size Justification

The treatment will be considered unsafe if a 2-year serious toxicity rate exceeding 10% cannot be excluded with the 95% interval. Serious toxicity in this study is defined as toxicity greater than grade 2 using CTCAE v4.0 criteria. To be scored as a serious toxicity counting toward the primary endpoint, the toxicity must have a “probable” or “definite” attribution to the study treatment. In a cohort of 200 patients, there should be 11 or fewer serious toxicities to exclude a rate of 10% using the upper limit of the 95% confidence interval.

The primary purpose of this trial is to ensure that the delivery of short-course accelerated partial breast irradiation (APBI) will result in a rate of serious toxicity that is similar to that reported for conventional fractionation schemes. Specifically, the treatment will be considered safe if we are confident that the 2-year serious toxicity rate doesn't exceed 0.10. Assuming that the probability of serious toxicities with the conventional procedure is 0.03, with a sample size of 200 patients, if we observe up to 11 serious toxicities, the upper 95% confidence limit will not exceed 0.10. The relative threshold toxicity rates for different sample sizes has been generated and is available for review from the PI.

A secondary endpoint is local control. We will follow patients until the last enrolled patient has a minimum follow-up of 2 years; thus the expected median follow-up of the study population will be 3-4 years. This will allow for a Kaplan-Meier estimate of local control at 3 years. We expect local control to be greater than 95%.

In addition to toxicity, cosmesis will be followed and evaluated as a secondary endpoint. Cosmesis will be evaluated by determining the number and percent of patients within each response category (Excellent, Good, Fair, Poor) at yearly intervals. Additionally, calculating the distribution of responses after collapsing into Excellent/Good versus Fair/Poor categories will be performed. Associations between dichotomous cosmetic outcomes (Excellent/Good versus Fair/Poor) and treatment related variables will be explored.

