### **Serious Adverse Event (SAE)**

A serious adverse event is defined as follows:

- 1) Death or threat to life;
- 2) Permanent impairment of a body function or permanent damage to a body structure; or
- 3) Requires medical or surgical intervention to preclude permanent impairment of a body function or permanent damage to a body structure.
- 4) Requires unexpected inpatient hospitalization or prolongation of existing hospitalization

**All serious adverse events are to be reported to the Rutgers Cancer Institute's Office of Human Research within 5 days of learning of the adverse event.**

Examples of serious events include: necrosis, non-wound healing, moist desquamation (that does not resolve within 4 weeks), unresolved bleeding, infection requiring medical or surgical intervention, pneumothorax, acute pneumonitis, seroma/hematoma (symptomatic and/or cosmetically deforming), rib fracture, severe pain (not resolving within the first month and requiring narcotics) and wound dehiscence.

Events not considered serious include: erythema, infection (or suspected infections, i.e., fever) treated only with antibiotics, and seroma/hematoma (asymptomatic and/or not deforming).

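### Fat necrosis is left out of the primary safety endpoint at every severity, so the safety conclusion is silent on a toxicity that the protocol's own rationale relies on

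*Combined protocol and SAP*

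**What the plan says.** **The endpoint.** Section 15.3 (also 1.4.1 and 5.1.1) states: "Serious toxicity in this study is defined as toxicity greater than grade 2 using CTCAE v4.0 criteria". Sections 11 and 15.3 add that attribution to treatment must be probable or definite. The decision rule is: "The treatment will be considered unsafe if a 2-year serious toxicity rate exceeding 10% cannot be excluded with the 95% interval". In 200 patients this is said to allow at most 11 events.

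**The exclusion.** Section 11.4 asks for detection, symptoms and treatment of fat necrosis at each visit, then closes: "Fat necrosis however is not a CTCAE toxicity and will not contribute to the endpoint analysis".

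**The rationale.** Section 2.4 says of the single-dose electron trial: "Significantly higher rates of fat necrosis were seen with ELIOT" (14% versus 7%). It contrasts that 14% with 2.3% for balloon-based treatment, attributes the excess to the dose, and names higher toxicity as one of two reasons for pessimism. It also reports fat necrosis in 18% of a 45-patient two-day series and in 2 of 30 patients in the investigators' own first cohort.

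**The data collected.** CRF #4 has a fat necrosis box, a treatment list that includes surgical excision, a five-level attribution item, an SAE flag, and a grade field (1 to 4, or not applicable). CRF #5, which sets out the CTCAE criteria, has no fat necrosis row. Appendix 4 says: "Examples of serious events include: necrosis, non-wound healing, moist desquamation", without naming a type of necrosis.

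**The concern.** The protocol argues against one large-fraction schedule partly on fat necrosis, then tests another large-fraction schedule with an endpoint that cannot register it. The reason given is that CTCAE has no such term. That explains why a grade is hard to assign, but not why a case serious enough for surgery should be invisible to the conclusion.

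The contrast with seroma is plain. On CRF #5, a symptomatic seroma for which operative intervention is indicated is grade 3 and counts if attributed to treatment. Fat necrosis treated by excision does not count in its own right.

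No analysis, threshold or table for fat necrosis is specified elsewhere in Section 15. The trial could therefore declare the schedule safe without any planned statement on this toxicity. A severity definition chosen after the data are seen would carry little weight.

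**Working it through.** **Inputs.** n = 200, limit 10%, maximum 11 events, and assumed conventional serious toxicity rate 0.03 (all Section 15.3). Fat necrosis of any severity: 2.3% (Section 2.3); 14%, 18% and 2/30 (Section 2.4). The rate of severe fat necrosis is not in the documents.

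**1. The plan's own figure.** The interval method is not named. The two-sided exact (Clopper-Pearson) upper limit for x events is the 0.975 quantile of Beta(x + 1, n − x):

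- x = 11: Beta(12, 189) gives 0.0963, below 0.10.
- x = 12: Beta(13, 188) gives 0.1025, above 0.10.

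Wilson (0.0958, 0.1019) and Agresti-Coull (0.0968, 0.1029) also give 11. The rule's arithmetic is sound; the question is what enters the count.

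**2. How many uncounted patients would reverse the conclusion.** At 3%, expected counted events are 200 × 0.03 = 6. Using 3% for this schedule is an assumption, since the plan states it for conventional treatment.

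- 6 + 5 = 11: upper limit 0.0963, still passes.
- 6 + 6 = 12: upper limit 0.1025, fails.

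Six additional patients, none already counted for another event, would be needed.

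**3. Six against the any-severity rates.**

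| Rate in documents | Expected cases in 200 | Share that six would be |
|---|---|---|
| 2.3% | 4.6 | more than all of them |
| 2/30 | 13.3 | 45% |
| 14% | 28 | 21% |
| 18% | 36 | 17% |

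**4. Assumed range for the severe rate.** Let q be the proportion of patients whose only severe event is fat necrosis, and hold the counted rate at 3%. As written, the probability of meeting the rule is P(X ≤ 11) for X ~ Binomial(200, 0.03) = 98.2%, whatever q is. If those patients counted, the rate would be 0.03 + q:

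| q (assumed) | Combined rate | P(X ≤ 11) |
|---|---|---|
| 0 | 3% | 98.2% |
| 1% | 4% | 89% |
| 2% | 5% | 70.0% |
| 3% | 6% | 45.8% |
| 5% | 8% | 11.7% |
| 7% | 10% | 1.7% |

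The table shows sensitivity to q. It does not estimate q.

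**5. What the earlier cohorts say about q.** None of the 45 patients and none of the 30 had grade 3 toxicity. The exact two-sided upper limit for zero events is 1 − 0.025^(1/n): 7.9% for 45, 11.6% for 30, and 4.8% for the 75 pooled. So the cohorts point to a low q without pinning it down, and they used 7 Gy × 4 rather than the present schedule.

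**The case against.** There is a fair case for leaving the endpoint alone.

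- **The choice is disclosed and the data are kept.** Section 11.4 gives its reason openly. Sections 11.6 and 11.7 also set telangiectasia and pigmentation aside. Section 7.6 requires fat necrosis to be reported at each visit, and Section 14.3 gives the DSMB a toxicity assessment at least every six months during accrual and treatment. This stands: the gap is in the conclusion, not the record.
- **Some severe cases enter by another route.** A reader might infer that anyone operated on for fat necrosis is scored as free of serious toxicity. The documents do not support that. Grade 3 pain, grade 3 infection, or grade 3 skin ulceration (whose CRF #5 definition includes necrosis of subcutaneous tissue) would still count. Only patients with no such event are missed.
- **Appendix 4 is weak evidence.** A reader might infer that it classes fat necrosis as serious. It says only necrosis, among skin and wound events, and governs reporting rather than the endpoint.
- **The earlier series cuts both ways.** Only grade 1 and 2 toxicities were reported where fat necrosis reached 18%. That suggests it was graded there, on a scale the protocol does not state, but none of those cases would have met a greater-than-grade-2 rule.
- **The cited rates come from more intense schedules.** With the protocol's alpha/beta of 4, 7 Gy × 4 has prescribed BED 28 × (1 + 7/4) = 77, against 64.5 in the Section 2.6 table for this schedule.

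None of this supplies a planned statement on severe fat necrosis, which is the narrower point that remains.

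**Conclusion.** The point holds as a gap in what the safety conclusion covers. Section 11.4 removes fat necrosis at every severity, the rationale treats it as important, and no other analysis picks it up. Patients whose only severe event is fat necrosis are not counted.

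Its size cannot be stated. The reversal from 6 to 12 events assumes a 3% counted rate and six severe cases in otherwise uncounted patients; the documents support neither number for this schedule. At the registry's 2.3%, the expected 4.6 cases would not reverse the conclusion from 6 events even if all were severe. With none severe, nothing changes.

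A reader might go further and infer that the safety verdict is biased downward, or that the true chance of passing is far below the nominal one. The documents do not support that. The drop in probability depends wholly on an assumed q. Nor does the protocol say whether its 3% reference and 10% limit include fat necrosis. If both exclude it, the rule is a narrower but consistent comparison. This is a reason to keep the primary rule and add to it.

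**What to change.** Leave the primary endpoint, the rule and the sample size as they are. Add to Sections 15.3 and 15.6 a pre-specified supportive analysis that:

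1. starts from the patients counted in the primary endpoint;
2. adds patients with fat necrosis recorded on CRF #4 as treated by surgical excision, with the same two-year window and the same requirement of probable or definite attribution;
3. counts each patient once;
4. re-applies the same 95% upper-limit calculation and reports both counts and limits with the safety conclusion.

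Surgical excision should be the trigger because CRF #5 gives no criteria for grading fat necrosis and CRF #4 allows the grade to be not applicable. A grade 3 or higher trigger should be added only if a grading definition is written before the data are examined.

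Reconcile Section 11.4 with the CRF #4 grade field, and state whether necrosis in Appendix 4 includes fat necrosis. CRF #3 item 11 offers only its Other line for fat necrosis, although Section 7.6 requires it at each visit; a dedicated line would make the count more reliable.

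The cost is one extra table from fields already on CRF #4, plus a written grading definition if that route is chosen. The downside for the sponsor is a second rate that is equal to or less favourable than the first.

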### **11.5 Pain**

Investigators are asked to record information regarding pain at each follow-up visit. Pain will be evaluated for (1) location, (2) degree and extent of pain, and (3) method of treatment, and scored per CTCAE v4.

### **11.6 Telangiectasia**

Patients will be evaluated for telangiectasia at each follow-up visit. Telangiectasia will be graded 1-4 (Grade: 1 = less than 9 cm^2, 2 = 9-36 cm^2, 3 = greater than 36 cm^2, and 4 = whole field). Telangiectasia is not considered a serious toxicity.

### **11.7 Pigmentation**

Patients will be evaluated for skin pigmentation at each follow-up visit. Pigmentation will be graded 1-2 (Grade: 1 = localized, <10% BSA, 2 = generalized, >10%). Pigmentation is not considered a serious toxicity.

## **12. COSMESIS**

Cosmesis, along with toxicity, is a secondary endpoint of the study and will be assessed in several ways. In general, the assessment tools have been adapted from the current NSABP-B39 study of APBI vs. WBI, and the UK altered fractionation study discussed in Section 2.4. The 3-year evaluation of cosmesis will serve as the cosmetic endpoint.

### **12.1 The Breast Cancer Treatment Outcome Scale (BCTOS)**

This is a self-report instrument that has high reliability and validity and will be used for evaluating patient-rated cosmesis at baseline (at time of informed consent) and at 2 years (see Appendix 7).

### **12.2 The Harvard Cosmesis Scale**

The Harvard Cosmesis Scale is a physician-rated form based and will be used by the treating physician (surgeon or radiation oncologist) to score cosmesis at baseline (at time of informed consent) and then annually until 2 years.

Excellent: treated breast looks essentially the same as the contralateral breast as it relates to radiation effects

Good: minimal but identifiable radiation effects of the treated breast

Fair: significant radiation effects readily observable

Poor: severe sequelae of breast tissue secondary to radiation effects

### **12.3 Frontal Digital Photographs**

Optional frontal digital photographs of both breasts will be taken at the time of consent, immediately before radiotherapy, and then annually. Two photographs will be taken, one prior to beginning treatment (preferably, prior to device placement) and one at the 2 year follow up visit. The photographs will be taken with the arms resting on the hips; they will be taken from the neck down and will not capture the face. Images will be taken by the treating physician using a dedicated camera belonging to the Radiation Oncology department. The images will be uploaded to Oncore (secure data capturing system), linked to the subject's case report forms and labeled with subject ID number and date of photo. Once images have been uploaded to Oncore, all other files can be destroyed. Comparisons of the baseline (before radiation) images and the photographs from year 2 will be scored on a 3-point scale: none/minimal change=0, mild=1, marked=2. One non-treating physician and one nurse will score each set independently.

Discrepancies will be resolved by consensus.

### **13. ETHICAL CONSIDERATIONS**

#### **13.1 Risks Associated with the Use of Brachytherapy Applicators**

##### **13.1.1 Surgery**

Complications associated with the surgical implantation of this applicator are similar to any tumor removal surgery with the implant of a post-surgical drain. Possible complications include, but are not limited to: infection, bleeding, loss or impairment of nerve function, swelling (edema), hematoma, fluid accumulation, wound effusions, wound breakdown, ecchymosis, and scarring.

##### **13.1.2 Applicator Implantation**

Complications arising from implantation of the applicator include, but are not limited to: infection, bleeding, loss or impairment of nerve function, swelling (edema), hematoma, fluid accumulation, applicator migration, and histotoxic reactions. Device malfunction may occur after placement requiring the placement of a second replacement device or alternative treatment.

##### **13.1.3 Brachytherapy Delivery**

Complications arising from the delivery of brachytherapy (radiation treatment) include, but are not limited to: infection, loss or impairment of nerve function, swelling (edema), scarring, skin effects including dry/moist desquamation, hyperpigmentation, telangiectasia and radiation induced necrosis.

##### **13.1.4 Imaging Procedures**

As part of the clinical study patients will undergo both x-ray and ultrasound procedures and are subject to the associated risks. The risks associated with these procedures are minimal to non-existent.

#### **13.2 Minimization of Risks**

Although the risks outlined in Section 13.1 may occur, the likelihood of serious events occurring is considered uncommon. The potential risks have been minimized by:

Performing complete validation testing of the applicator; implementing appropriate quality measures into the production; and providing adequate directions for use in the labeling.

Physicians who receive the applicator practice within an institution that has completed the required physics training and are experienced in the field of oncology, surgery, and radiation therapy, which will help to minimize the risk to the patients involved.

Guidelines for patient selection and evaluation are intended to prevent the inclusion of patients who might be prone to injury due to this study, or who are inappropriate candidates for other reasons.

